5.3 Study Drug Supply, Accountability And Preparation

The investigational research pharmacy at each clinical site will be responsible for purchasing and mixing the UFH from stock solution or powder to the appropriate concentration (100 units per mL) into an intravenous saline infusion bag. Pharmacies also have the choice to purchase premixed unfractionated heparin from a manufacturer, as long as the concentration is equal to 100 units per mL. Optimal cost-effective management of the study drug would involve mixing a 250 or 500 ml bag that would last approximately 24 hours (UFH in 0.9% or 0.45% saline at 100 units per mL).

The heparin solution, infusion bags, IV tubing, will be supplied by the standard vendors within each participating institution, and tracked per that individual institution's specific policies and procedures. These supplies are needed above and beyond the normal SOC and therefore should not be billed to insurance. The study subject ID number, patient name, and site specific medical record number will be on the study drug label prepared by the investigational pharmacy so that if two subjects are enrolled simultaneously at a clinical site the subjects will always receive the proper study drug.

5.4 Study Drug Blinding Procedure

Physicians, residents, nurses, and clinical staff providing clinical care during the acute hospitalization of the study subjects will be aware of the treatment allocation (unblinded) and as a result will be monitoring for safety concerns related to prolongation of coagulation parameters (aPTT and anti-Xa), thrombocytopenia, bleeding, development of DVT or PE, or other AEs or that might be related to the patient's treatment allocation (LDIVH vs. SOC).

The investigational pharmacy at each site will properly label the study drug infusion bag with all of the information including patient name, site specific medical record number, study site ID#, study patient ID#, and study drug concentration.

The study team members conducting the neurological and cognitive assessments during the 90- day and 1- year follow-up visits will remain blinded to treatment allocation. The patients will be instructed not to reveal their treatment allocation. All imaging will be de-identified and coded in a HIPAA compliant manner with the patient's study ID # and date of scan but without any other information that would allow the core imaging lab to identify the patient identity, treatment allocation or dose. The biostatistician will be aware of two treatment groups but will not be aware of

whether the group was treated with UFH during interim analysis for the DSMB unless the DSMB determines it is necessary to unblind for safety purposes. The final statistical analysis will be performed in an unblinded fashion but rigorous methodology will be utilized. The study team members conducting imaging verification and the biostatistician will not have direct patient contact so accidental disclosure by the study subjects themselves should not occur.

5.5 Treatment Compliance And Drug Accountability

Daily documentation in the patient's eCRFs that attest to the patient receiving the study drug infusion, and the rate of the study drug infusion is required for those randomized to the LDIVH arm. The investigational pharmacy will prepare each study drug infusion bag.

5.6 Treatment Of Study Drug Overdoses

If a study subject has received a study drug overdose, the infusion will be stopped and the patient monitored until it is determined that it is safe to resume the drug. If deemed necessary by the attending study physician labs (aPTT) will be monitored to ensure patient safety and restarted when deemed appropriate. The overdose, relevant labs, and study drug start/stop times will be recorded in RedCap under Protocol Deviations.

6. STUDY PROCEDURES: SCREENING THROUGH DISCHARGE FROM THE ACUTE CARE SETTING

6.1 Screening

Potential study patients will be considered to be in the screening process as soon as research personnel are notified of a potential study candidate. The potential study subjects screened will be patients presenting with a likely diagnosis of aSAH. They will be considered to be in screening until the patient is either randomized and enrolled or excluded from participation in the trial by inclusion/exclusion criteria or lack of informed consent. Screening may begin before or after the aneurysm coiling procedure.

Patients referred to study personnel presenting at participating institutions with a suspected diagnosis of aSAH will be considered potential study subjects. Study personnel will review the eligibility criteria to determine if they are candidates for this trial. Relevant snapshots of the initial head CT scan will be uploaded into Oculus imaging by the site coordinator to be reviewed by the study PI or designee and verify modified fisher grade. An alternative option is to send de-identified snapshots of the CT scan by other electronic means, such as text message.. Please see section 4.1 for detailed information on the Modified-Fisher Score including example images. The WFNS SAH scale scores are to be performed by properly trained study personnel. Please see section 4.1 for detailed information on the WFNS SAH Scale. If the patient qualifies, the patient, and/or the patient's legally authorized representative (LAR) will be approached by a designated study team member to begin the informed consent process

and be given the opportunity to participate. The patient is considered “enrolled” after they have been randomized to a study treatment allocation.

All subjects admitted with the diagnosis of non-traumatic SAH should have basic, de-identified data entered into a screening log at each institution. This will require the study team to interact with the clinical ICU and/or neurosurgical team at least daily to identify these patients (in person or by phone). A log will be maintained and the specific reason(s) for each non-enrolled potential subject who either fails to meet criteria, refuses participation, or deemed by the clinical treating team to ineligible for study due to reasons not pre-specified. These logs will be maintained at each institution and electronically entered to a central database that will maintain a log for all centers involved in the study. These logs will be reviewed on a regular basis by the PPI ([name]) to assess whether sites are meeting recruitment goals and to determine whether there are any systematic reasons for non-enrollment that may bias the study outcomes.

6.2 Informed Consent

The principles of Informed Consent, according to FDA Regulations and the International Conference on Harmonisation (ICH) guidelines on Good Clinical Practice (GCP) will be followed. Investigators and research personnel will complete CITI training (Collaborative Institutional Training Initiative; <https://www.citiprogram.org/>) related to these guidelines as a method to document their familiarity and understanding of these guidelines. CITI certificates for all members of each site’s study team will be forwarded to the clinical coordinating center (University of Louisville). The informed consent form will be approved by the IRB at each site prior to any patient enrollment at that site. All study subjects must have informed consent to participate and only the participant and/or the participant’s legally authorized representative (LAR) may provide consent. The consent document is to be cosigned by the study team member obtaining informed consent at the time of the initial consent process when the patient and/or LAR sign the document. A study investigator may sign the consent document at a later time if they were not the one conducting the initial informed consent process, but this is not required.

Study treatments or procedures will not begin, and data will not be collected for study purposes until consent has been obtained. Informed consent may be obtained before or after the aneurysm coiling procedure. If consent is obtained prior to the aneurysm coiling procedure, the patient will be randomized and enrolled following the procedure assuming they continue to meet the enrollment criteria. Enrollment is not intended to occur at the time that informed consent is obtained but rather ONLY after confirmation that the patient meets enrollment criteria and has been randomized to a treatment allocation. There may therefore be patients who have provided informed consent to participate in this study whom are never actually enrolled in the study. These patients should be informed of this event if it occurs. In the event of screen failure, patients will be assigned a screening ID number and basic, de-identified information will be entered into a separate REDCap database to document the reason for screen failure.

It is intended that the informed consent will be obtained by a member of the research team in as private a place as possible. It is intended that the informed consent document will be reviewed by a member of the research team with the patient and/or a legally authorized representative (LAR). Any questions that the patient or LAR have will be answered to the best ability of the research team member. It is intended that the patient / LAR will be given sufficient time to review the consent document and ask further questions. It is intended that the person obtaining informed consent will ask the patient / LAR questions to assure understanding. If the patient / LAR agrees to participate, the patient / LAR will be asked to sign the consent document. It is intended that a copy of the consent will be given to the patient / LAR and the original, signed Informed Consent Document (ICD) will be kept in the study records. Special care will be taken with the consent process as we are targeting a vulnerable population for our study sample. Patients and LAR will be instructed that they can withdraw from the study at any time for any reason without any change in the standard of care treatment of their medical problem.

For potential study subjects / LARs with limited or low literacy, it is intended that the consent will be read aloud to the patient and explained at the appropriate level. It is intended that questions will be asked by the study team member obtaining informed consent to ensure understanding. Questions from the patient / LAR will be encouraged. Cognitive impairment and decision-making ability will be determined by the research team member obtaining consent based on patient history, history of present illness, medications, presentation, stroke scale, etc. It is intended that identification of the LAR will follow the general statutes in place, as well as policies dictated by the institution. We recognize that if a LAR has been utilized to obtain consent, at a future encounter with the participant the research team will continue to educate the subject regarding the research, and it is intended that the research team will periodically verify the subject's wish to either continue their participation or exit from the study.

Those who do not speak and / or read English will be accommodated with an institutionally approved short-form and a foreign language interpreter. When deemed appropriate, we will seek translation of the informed consent document into other languages. Cultural and social considerations will be made including spending the time necessary for patients and their family to consider participation. Pastoral care services available at the hospital will be utilized when appropriate based on patient and family needs and requests.

The rights, safety, and well-being of trial subjects are the most important considerations and will prevail over the interests of this study, the investigators, science, and society.

6.3 Final Screening Following Informed Consent And Aneurysm Securement

A CT scan of the head obtained between 2-12 hours after completion of the aneurysm embolization procedure is required prior to enrollment in the study. A head CT scan performed at some point after the procedure represents standard of care (SOC)

following aneurysm securement. The CT scan results are to be reviewed by a physician investigator and/or neuroradiologist. If there is an indication on this CT of findings that would exclude the patient from enrollment (see exclusion criteria section 4.2) then the patient will not be enrolled.

If the patient remains eligible as indicated by meeting all enrollment criteria including appropriate findings on their post-procedure CT, and informed consent has been obtained, the patient will be randomized. If the patient has not yet been consented, the informed consent process will begin at this time with the patient and / or LAR. If consent is granted, the patient may be randomized.

6.4 Randomization Procedure

The randomization will be a blocked-stratified randomization scheme. We considered 4 factors for stratification to ensure equal distribution of factors between treatment groups: age, aneurysm location, gender, and clinical site. As age increases above 70 years old the risk for undiagnosed dementia increases and this could have a significant confounding result on our primary efficacy outcome of cognition (MoCA score). As a result we elected to limit enrollment to 70 years old or less to eliminate the need for age stratification. Given we will have 8-10 clinical sites, stratification of randomization by site would be difficult to implement while controlling for other more important factors and therefore we will do post-analysis statistical controlling for clinical site. Finally we elected to stratify with just two factors sex and aneurysm location. Aneurysm location will be a binary stratification of anterior communicating artery (ACoA) aneurysm versus all other locations. This was done because of previous reports that ACoA location SAH has a higher risk of cognitive disability than other locations and our own preliminary human data that suggests the same. Block sizes will fall within the range of 4-10 but will not be disclosed in this protocol to prevent any bias related to patient selection by investigators.

A member of the study team can randomize post-coiling subjects with informed consent who continue to meet the eligibility criteria. Patients will be randomized to one of two treatment allocation (LDIVH or Control) groups. A blocked-stratified randomization table will be created prior to initiation of the study. The REDCap database will utilize this to select treatment allocation. If the randomization feature of the EDC system is non-functional, the subject will be randomized by telephone call to the clinical coordinating center (ASTROH Project Manager). Patients should not be randomized until it is determined the patient meets all eligibility criteria, has undergone the informed consent process, AND it has been determined by the post-procedure head CT scan that the patient is still eligible to participate.

6.5 Enrollment Of Subjects

Patients are considered enrolled in the trial once they are randomized to a study treatment allocation.

6.6 Collection Of Baseline Patient Information

[May occur prior to enrollment, during screening process and may be completed after enrollment for those items not related to eligibility]

During screening, after informed consent has been obtained, or following enrollment baseline information may be collected.

The CRFs for this trial were developed as modifications of the stroke modules provided by the NIH/NINDS common data elements (CDEs) for clinical trials program.

Clinical and historical assessments will include: historical pre-morbid mRS, Assessment for Dementia and pre-morbid employment status. Assessments of NIHSS and MoCA, having occurred immediately prior to enrollment or soon after enrollment.

Baseline biomarker specimens will be obtained after enrollment but prior to initiation of study drug or within 6 hours of initiating study drug.

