Peak and Overall Plasma and CSF levels of hsCRP at enrollment and, infusion days #2, 4, 6, and 10 compared between groups.

-SECONDARY CLINICAL EFFECT ENDPOINTS

Trail Making Test Parts A&B at 90 (± 10) days post enrollment.

MoCA at 1-year (± 30 days)

Center for Epidemiologic Studies Depression Scale (CES-D) at 90 (± 10) days post enrollment

Return to work status between groups at 90 (± 10) days

SECONDARY EXPLORATORY PRESPECIFIED BIOMARKER OUTCOMES

Plasma and CSF levels of IL-6, TNF- α , P-Selectin, sICAM-1, HMGB-1, MRP8/14 plasma levels at enrollment and infusion day #2, 4, 6, and 10

ADDITIONAL PRE-SPECIFIED

Rate of MoCA ≤ 20 between groups at the 90-day follow-up visit.

**EXPLORATORY
OUTCOME ANALYSES**

In-hospital incidence of any fever ($> 38.3^{\circ} \text{C}$; $\geq 101.0^{\circ} \text{F}$), Incidence of multiple fever episodes (≥ 3), and Mean Daily Fever Burden.

GCS and NIHSS at enrollment and infusion days # 2,4,6,10, discharge and 90 (± 10) days

MoCA at post-enrollment day #1, 6 and 10

Correlation analysis between MoCA scores and inflammatory biomarker levels with and without adjusting for hemorrhage burden (Hijdra Sum Score).

Incidence of moderate and severe Radiographic Cerebral Vasospasm based on a CTA, MRA, or Catheter DSA obtained between PBD # 6-12 as determined by an independent and blinded core imaging lab.

Incidence of TCD criteria for significant vasospasm (velocities $>200 \text{ cm/s}$ and / or MCA / ICA (Lindgaard) ratio >6)

Incidence of TCD criteria for absence of vasospasm (velocities $<120 \text{ cm/s}$)

Incidence of clinical vasospasm requiring rescue therapy (eg, pressors, endovascular treatment)

Incidence of "Delayed Cerebral Ischemia" defined as:

- Symptoms of neurological deterioration (e.g. hemiparesis, aphasia, decreased level of consciousness)
- Symptoms last for more than an hour
- Symptoms are not explained by other physiological processes (e.g., hydrocephalus, hypotension)

CT or MRI evidence of Vasospasm Related Cerebral Infarction on post-infusion (discharge) imaging as scored by an independent and blinded core imaging lab

Global outcome as measured between group ordinal regression analysis of the modified Rankin Scale score at 90-days and 1-year.
Return to work status between groups at 1-year.
Lawton IADLs at 90 (± 10) days
QOLIBRI-OS at 90 (± 10) days and 1-year.
Checklist Individual Strength-subscale Fatigue (CIS-f) at 90 (± 10) days
Barthel Index at 90 (± 10) days and 1-year

**INVESTIGATIONAL

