STUDY DRUG NAME
AND FORMULATION**

Unfractionated Heparin (UFH) intravenous solution at a concentration of 100 units per ml (25,000 to 50,000 units of heparin in 250 to 500 ml of 0.9% or 0.45% NaCl solution)

INTENDED USE

A prophylactic infusion of LDIVH for up to 14 days with prescribed escalated dosing until the goal aPTT value is achieved. The LDIVH infusion is intended to prevent cognitive deficits in modified-Fisher grade 3 and 4 aneurysmal subarachnoid hemorrhage survivors following endovascular coil embolization of the ruptured cerebral aneurysm. The LDIVH infusion is to be initiated 12 ± 4 hours after coiling of the aneurysm. The infusion will be started at 8 units/kg/hr (0.08 cc/kg/hr) and increased by 2 units/kg/hr every 12 hours until the goal aPTT is reached (typically 12 u/kg/hr) *Note: The goal aPTT is an institution specific aPTT value that correlates with an anti-Xa assay value of 0.1 – 0.3 IU/ml of heparin.*

STUDY SUCCESS

For the purposes of this trial, study success is defined as demonstrating a statistically significant improvement in the mean MoCA score for the LDIVH arm compared to the control arm of the study at the 90-day follow-up visit or a significant reduction in inflammatory biomarker levels in the LDIVH arm compared to the control arm. In addition, there can be no significant differences between groups in the rate of Major Bleeding or Clinically Relevant Non-Major Bleeding attributable to the LDIVH treatment.

PATIENT COMPLETION

Patient completion in the study occurs when the patient has completed his/her 1-year follow-up

visit and all case report forms (CRFs) and Imaging required by the Study Protocol have been completed OR the patient has withdrawn from the study or has been determined to be “Lost to Follow-up” and all available CRFs and Imaging have been collected and submitted to the University of Louisville. The primary endpoint is the 90-day follow-up visit and therefore the primary data-analysis will occur after this date.

**PRIMARY PRINCIPAL
INVESTIGATOR (PPI) /
SPONSOR**

[name]
Associate Professor of Neurosurgery
Chief, Vascular Neurosurgery
University of Louisville School of Medicine
Louisville, KY
[contact];
[contact]

**CO-PRINCIPAL
INVESTIGATORS (Co-PI)**

J. [name], PhD
Professor of Neurosurgery, Pathology & Physiology
University of Maryland Medical Center
Baltimore, MD

[name]
Professor and Vice Chair for Education
Department of Neurosurgery
Director, Cerebrovascular Surgery Program

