Unfractionated heparin (UFH) is clinically utilized almost exclusively for its anticoagulant properties, yet heparin binding can interrupt numerous other biological pathways. Among its wide-ranging effects, heparin complexes with free hemoglobin itself, including oxyhemoglobin, blocks the activity of free radicals (FR) including reactive oxygen species (ROS), antagonizes endothelin-mediated vasoconstriction, binds several cytokines and all chemokines, thereby imparting potent anti-inflammatory effects. It is hypothesized that heparin may exert a therapeutic benefit in SAH patients by acting via one or more of these well-established anti-inflammatory mechanisms.

Recently, experiments utilizing a rat model of SAH, found that continuous intravenous administration of unfractionated heparin was able to downregulate neuroinflammation and prevent neurodegeneration, demyelination, and transynaptic apoptosis.

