6.7 Baseline Blood And Biomarker Specimen Collection

Please draw all normal blood tests as you would for your normal standard of care for the treatment of an aneurysmal subarachnoid hemorrhage. hsCRP and Anti-Xa levels will be drawn for all subjects after enrollment but prior to initiation of the study drug (for those subjects in the LDIVH treatment group).

Additional blood will be drawn and processed to plasma and stored for additional biomarker analysis. This may be performed up to 6 hours after initiation of study drug for the LDIVH arm (but preferably prior to study drug initiation). Please see the section below on the collection and processing of plasma biomarker specimens Section 6.11

If the subject already has an external ventricular drain or a lumbar drain placed, then removal of cerebrospinal fluid should be performed again with processing of the specimens for biomarker analysis. This may be performed up to 6 hours after initiation of study drug for LDIVH arm (but preferably prior to study drug initiation). Please see the section below on the collection and processing of CSF biomarker specimens Section 6.11.

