6.11 Inflammatory Biomarker Collection and Processing

hs-CRP blood levels will be drawn and processed by each site's clinical laboratory and the results of these tests will be documented in the database CRFs for each time point which will include time of enrollment, and post-enrollment days #2, 4, 6, and 10. As such, these values will be immediately available to the DSMB and Steering Committee during the interim analysis.

hs-CRP levels will be measured in the CSF as well. CSF will be sent to the local institution's lab for analysis of hs-CRP in the appropriate tube per the lab's standard procedure.

Additional blood and CSF (when a drain is present) will be drawn at enrollment and post-enrollment days # 2, 4, 6 and 10. The blood and CSF will be processed and stored locally and then shipped to the biomarker core lab for further planned biomarker analysis to be processed in a batch fashion after all samples have been collected. Currently the planned biomarkers to be analyzed include: IL-6, TNF- α , P-Selectin, ICAM-1, HMGB-1, and MRP 8/14.

Biomarker processing kits will be mailed to each site that will include instructions, transfer pipettes, shipping packaging, specimen box, pre-filled labels, and other supplies necessary to process blood to plasma and store them in the -70°C freezer. Each site will need to supply venipuncture supplies (needles, vacutainer tubes, or butterfly needles). Each site will also need to supply their own centrifuge, ice bucket, dry ice, and -70°C freezer space.

Collection of Biomarker Blood Specimens and Processing to Plasma:

1. **Collect 9-10 ml of venous blood** using a lavender top Vacutainer (EDTA). Mix according to standard guidelines. If collecting blood from an IV, PICC, or other line, make sure there are no medications hooked up to the line (such as heparin), if there are, temporarily turn off these infusions and waste at least 5 cc of blood prior to collecting the specimen. Turn infusions back on at the same rate following the blood draw.
2. **Within 30 minutes of the blood draw, centrifuge the tube for 10 min at 500g** (approx. 2,000 rpm in a standard centrifuge). If samples cannot be processed within 30 minutes, the tubes should be kept on ice until they can be centrifuged (*no more than 2 hours delay*). **Do NOT freeze the whole blood samples!** Heavily hemolysed or lipemic samples are to be avoided.

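### Some enrollment plasma and CSF biomarker specimens may be drawn up to 6 hours into the study infusion, in the LDIVH arm only, and sections 6.6 and 6.7 conflict on whether this extends to hsCRP

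*Protocol*

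**What the plan says.** Section 6.6 gives one rule for every baseline biomarker: "Baseline biomarker specimens will be obtained after enrollment but prior to initiation of study drug or within 6 hours of initiating study drug".

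Section 6.7 gives two. For hsCRP and anti-Xa it says "hsCRP and Anti-Xa levels will be drawn for all subjects after enrollment but prior to initiation of the study drug". For the additional blood that is processed to plasma and stored it says "This may be performed up to 6 hours after initiation of study drug for the LDIVH arm (but preferably prior to study drug initiation", and it repeats that allowance for CSF in subjects who already have a drain.

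Section 6.11 lists what the core laboratory will measure: "Currently the planned biomarkers to be analyzed include: IL-6, TNF- α , P-Selectin, ICAM-1, HMGB-1, and MRP 8/14". The synopsis (section 1.1) classes these markers as exploratory. Section 6.11 adds that "hs-CRP levels will be measured in the CSF as well", by the site's own laboratory.

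The primary biomarker endpoint in section 1.1 is "Peak and Overall Plasma and CSF levels of hsCRP at enrollment and, infusion days #2, 4, 6, and 10 compared between groups", so it covers both fluids and names the enrollment value. The study-success definition in the same section accepts a better MoCA "or a significant reduction in inflammatory biomarker levels in the LDIVH arm compared to the control arm". Section 1.2.2 also plans a subgroup split on elevated versus normal hsCRP at enrollment.

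**The concern.** A baseline value should not depend on the treatment that it is used to assess. Controls receive no study infusion (section 6.8), so only LDIVH subjects can contribute an enrollment specimen taken during one. A measurement rule tied to the arm is not balanced by randomization.

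The protocol itself does not treat 6 hours as a drug-free interval. Section 5.2 orders an aPTT at 6 hours to see whether a therapeutic level has been reached, and in the worked example of section 6.8 the 6-hour aPTT of 42 seconds already lies inside that site's 40–60 second target. The rationale in section 2.1 is that heparin "binds several cytokines and all chemokines, thereby imparting potent anti-inflammatory effects". An effect of that kind could appear early, although the protocol gives no data at 6 hours for any planned marker.

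If an early effect exists and the enrollment value is used as a reference, part of the treatment effect is absorbed into the LDIVH baseline. Biomarker reduction is one of two routes to declaring the study a success, so the enrollment value should mean the same thing in both arms. Separately, a site following 6.6 could draw enrollment hsCRP after the start of infusion in good faith, while a site following 6.7 could not.

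**Working it through.** The protocol states no figure on this point, so there is none to reproduce. The check is a comparison of the texts, followed by illustrative arithmetic.

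**Step 1. Which rule applies to which specimen in the LDIVH arm**

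| Specimen | Section 6.6 | Section 6.7 |
|---|---|---|
| Blood hsCRP | Before, or up to 6 h after start | Before start |
| Core-lab plasma | Before, or up to 6 h after start | Up to 6 h after start; before is preferred |
| Core-lab CSF | Before, or up to 6 h after start | Up to 6 h after start; before is preferred |
| CSF hsCRP | Before, or up to 6 h after start | Unresolved |

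The first row is a direct conflict on the primary biomarker. The last row is unresolved because the hsCRP sentence in 6.7 does not name the fluid and the CSF paragraph does not name the marker. The Schedule of Events (section 15.1) does not settle it: footnote A fixes the date of the baseline draw, not its order relative to the start of infusion.

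**Step 2. Heparin given by 6 hours**

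At the starting rate of 8 u/kg/hr (section 6.8), 8 × 6 = 48 u/kg. For the 80 kg example, 48 × 80 = 3,840 units.

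**Step 3. Where the enrollment value matters**

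- Raw between-arm comparison of days 2, 4, 6 and 10: unaffected.
- Change from enrollment, or enrollment as covariate: affected, as in step 4.
- Overall level including enrollment: affected in the other direction. An early fall would count toward the treatment difference.
- Peak level including enrollment: affected only in subjects whose enrollment value would be the highest.
- Enrollment-hsCRP subgroup: affected only if a site follows 6.6 for hsCRP.
- Check of comparability at enrollment: affected for the exposed markers.

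**Step 4. Illustrative size**

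Let *f* be the share of LDIVH subjects sampled after start, *d* the shift caused by the infusion at the time of sampling in SD units, and *b* the slope of the later value on the enrollment value. None is in the protocol; all are assumed. The mean LDIVH baseline moves by *f* × *d*, so:

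- bias in a change-from-baseline contrast = *f* × *d*
- bias in a baseline-adjusted (ANCOVA) contrast = *b* × *f* × *d*

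With 44 LDIVH subjects and *b* = 0.5:

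| *f* (subjects) | *d* | Change score, SD | ANCOVA, SD |
|---|---|---|---|
| 0.10 (4.4) | 0.1 | 0.01 | 0.005 |
| 0.25 (11) | 0.3 | 0.075 | 0.037 |
| 0.50 (22) | 0.3 | 0.15 | 0.075 |
| 1.00 (44) | 0.5 | 0.50 | 0.25 |

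If heparin lowers the marker early, the bias is toward no effect; if it raises the marker early, the bias is the other way. If every baseline specimen precedes the infusion, *f* = 0 and the bias from the study infusion is 0.

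**The case against.** The strongest case on the other side has five parts.

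- **The primary marker is mostly protected.** Section 6.7 is the specific section and requires hsCRP before study drug. The six other markers are exploratory, and CSF exists only where a drain is present. This stands. What remains for hsCRP is the contradiction in 6.6 and the open question on CSF.
- **The protocol states no change-from-baseline or baseline-adjusted biomarker analysis.** The endpoint is peak and overall levels compared between groups, and the biomarker mean in the fever analysis of section 6.12.6 omits enrollment. This stands, and it limits the harm to the uses listed in step 3 of the working.
- **Controls are not heparin-free.** They receive subcutaneous heparin, with no first dose timed against the draw (sections 3 and 6.12.5), and intravenous heparin around coiling is allowed in either arm (section 6.12.4). A reader might infer that the baseline is drug-exposed in one arm and drug-free in the other. The protocol does not support that. It supports only that exposure to the *study infusion* can occur in one arm. The allowance is also permissive, so LDIVH baselines may be exposed; it does not follow that they are.
- **Late specimens can be identified afterwards.** Draw time is on each cryovial (section 6.11) and infusion start time is in the CRF (section 6.8). This stands and makes the remedy easier. It does not reconcile 6.6 with 6.7, or change the fact that the protocol accepts the late specimen as the baseline.
- **A strict rule costs specimens.** The post-coiling CT falls at 2–12 hours and the infusion starts at 12 ± 4 hours after coiling, so the time between randomization and infusion can be short, and plasma must be centrifuged within 30 minutes or kept on ice for no more than 2 hours. This stands in part. The hsCRP and anti-Xa draw must fit the same interval anyway, so no extra venipuncture is needed.

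**Conclusion.** The point holds in limited form. Sections 6.6 and 6.7 allow enrollment specimens for the stored-plasma markers and for CSF to be drawn up to 6 hours into the study infusion, which only one arm receives. Section 6.6 also contradicts 6.7 on hsCRP, and the rule for CSF hsCRP is undetermined.

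The size cannot be computed from the protocol. The range of 0.01 to 0.50 SD for a change score, or 0.005 to 0.25 SD for an adjusted contrast with slope 0.5, rests wholly on assumed values of *f*, *d* and *b*, and applies only if the enrollment value is used in that way.

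Two further inferences are tempting and unsupported. A reader might conclude that the stated biomarker comparison is biased by a known percentage; no input for such a figure is given, and a raw comparison of post-baseline levels is not biased by this rule at all. A reader might also conclude that the arms cannot be compared at enrollment; pre-drug blood hsCRP under 6.7, the clinical and imaging baseline characteristics, and every biomarker specimen drawn before the infusion remain available for that.

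This is an avoidable asymmetry worth correcting. It does not threaten the MoCA endpoint or the sample size.

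**What to change.** - Reconcile section 6.6 with 6.7 so that hsCRP, in blood and in CSF, is drawn before study drug, and say explicitly that CSF hsCRP is covered.
- In 6.6, 6.7 and the Schedule of Events, have the core-lab plasma tube filled at the pre-drug draw that 6.7 already requires for hsCRP and anti-Xa, and take enrollment CSF before the infusion where a drain is present.
- Use the recorded draw and infusion-start times to code any later specimen as post-start. Keep it in the data, but do not count it as a baseline value.
- Record heparin exposure before the draw in both arms (procedural and subcutaneous), so that the comparison at enrollment can be interpreted.

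The cost is protocol wording and a line in the laboratory instructions, with no additional venipuncture. The downside is a few missing baseline values, mainly in the LDIVH arm and for mostly exploratory markers, when staff cannot collect or process the specimen before the infusion. The 2-hour on-ice allowance in section 6.11 limits that loss.
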